## Table 4: Toxicity Grading Tables – ECG

Note 1: Events will be coded as treatment-emergent SAEs if there are life-threatening associated symptoms or signs (arrhythmia, CHF, hypotension, syncope, TdP, etc.).

Note 2: If a male subject was accepted into the trial with a QTcF value that overlaps with values used for grading Grade 1 QTcF prolongation, a TEAE will be reported if the QTcF value is higher than the baseline value.

## **Appendix C: Blood Volume Withdrawn During the Trial**

Study Periods	Out- patient	In- patient	In- patient	In-patient Dosing Period (Days 1 – 3)				Out-patient			
Study Visit	Screen	Check- in	Baseline	Dosing	Follow-up Discharge		narge	Follow- up	Final	ET	
Study Day a	-28 to -3	-2	-1	1	2 (24 h)	2 (36 h)	3 (48 h)	3 (60 h)	14 (±3 days)	30 (±4 days)	
HEMATOLOGY 	4.0	4.0		4.0	4.0	4.0	4.0	4.0	4.0		4.0
CHEMISTRY and serum $\beta$ -HCG and FSH $^1$	8.5	8.5		8.5	8.5	8.5	8.5	8.5	8.5		8.5
COAGULATION 	2.7	2.7		2.7	2.7	2.7	2.7	2.7	2.7		2.7
TSH, Free T4, Free T3 	3.5	3.5		3.5	3.5	3.5	3.5	3.5	3.5		3.5
Viral Serology (HIV, HBsAg, HCV) 	7.0										
Exploratory Marker (serum Cystatin) 		3.5		3.5			3.5		3.5	3.5	3.5
PK 				56.0	8.0	8.0	8.0	8.0			8.0
Total volume/visit	25.7	22.2	0	78.2	26.7	26.7	30.2	26.7	22.2	3.5	30.2
Cumulative total volume	25.7	47.9	47.9	126.1	152.8	179.5	209.7	236.4	258.6	262.1	

## Table 5: Laboratory Samples and Estimated Total Blood Volume (mL)

a Study Days shown correspond to days in each study period. For a view of the cumulative numbering of study days, please refer to Section 7.

 Clinical Safety blood tests (HEM, CHEM, COAG, TSH, fT4, fT3) are drawn at Screening Visit, on Day -2, and on Days 1, 2, 3 and 14 (± 3 days), or ET. Serum pregnancy test in all women is drawn at Screening. FSH is drawn only at Screening in post-menopausal women.

 Viral serology tests are drawn at Screening.

 $^3$  Serum Cystatin test is drawn on Day -2, Day 3 (at 48 h) and Day 14 (± 3 days).

 PK plasma samples are drawn on Day 1 (30 min before dosing and at 0.5, 1, 2, 4, 8, 16 h after dosing); on Day 2 (24 and 36 h after dosing) and on Day 3 (48 and 60 h after dosing), or ET if occurs within 24 h of dosing.

# LIST OF ABBREVIATIONS

CLT	Total Clearance		
C max	Maximum Concentration		
COAG	Coagulation		
ConMed	Concomitant Medication		
CRF	Case Report Form		
CS	Clinically Significant		
CSR	Clinical Study Report		
CTU	Clinical Trial Unit		
CV	Coefficient of Variation		
ΔQTcF	Pre-dose, baseline difference in QTcF interval		
ΔΔQTcF	Time-matched, baseline-adjusted difference in QTcF interval		
dB	Decibel		
DBP	Diastolic Blood Pressure		
dL	Deciliter		
DMID	Division of Microbiology and Infectious Diseases		
DPOAE	Distortion Product Otoacoustic Emission		
ECG	Electrocardiogram		
eCRF	Electronic Case Report Form		
EDC	Electronic Data Capture		
eGFR	Estimated Glomerular Filtration Rate		
ELF	Epithelial Lining Fluid		
F	Fahrenheit		
FDA	Food and Drug Administration		
FEV1	Forced Expiratory Volume in the first second		
FSH	Follicle Stimulating Hormone		
FVC	Forced Vital Capacity		
g	Gram(s)		
GM	Geometric Mean		
h	Hour(s)		
HBsAg	Hepatitis B-virus Surface Antigen		
HCV	Hepatitis C-virus		
HEENT	Head, Eyes, Ears, Nose, and Throat		

HEM	Hematology		
HIV	Human Immunodeficiency Virus		
HLGT	High Level Group Term		
HPF	High-Powered Field		
HR	Heart Rate		
ICF	Informed Consent Form		
ICH	International Conference on Harmonisation		
IMP	Investigational Medical Product		
INR	International Normalized Ratio		
IUD	Intrauterine Device		
IV	Intravenous		
Ke	Elimination Rate Constant		
kg	Kilogram(s)		
kHz	Kilohertz		
KIM-1	Kidney Injury Molecule 1		
L	Liter(s)		
LC-MS/MS	Liquid Chromatography Tandem-Mass Spectrometry		
LLOQ	Lower Limit of Quantification		
Max	Maximum Value		
MedDRA	Medical Dictionary for Regulatory Activities		
μg	Microgram(s)		
mg	Milligram(s)		
MH	Medical History		
Min	Minimum Value		
mL	Milliliter(s)		
mmHg	Millimeters of Mercury		
mmol	Millimole(s)		
МОР	Manual or Procedures		
msec	Millisecond(s)		
Ν	Number (typically refers to participants)		
NCA	Noncompartmental Analysis		
NCS	Not Clinically Significant		

NIAID	National Institute of Allergy and Infectious Diseases		
NIH	National Institutes of Health		
ONR	Outside Normal Range		
OTC	Over the Counter		
PE	Physical Examination		
PI	Principal Investigator		
РК	Pharmacokinetics		
Protime	Prothrombin Time		
РТ	Preferred Term		
QNS	Quantity Not Sufficient		
QTcF	Corrected QT Interval of the ECG using Fridericia's Formula		
RBC	Red Blood Cell		
RR	Respiratory Rate		
SAE	Serious Adverse Event		
SAP	Statistical Analysis Plan		
SBP	Systolic Blood Pressure		
SD	Standard Deviation		
SDCC	Statistical and Data Coordinating Center		
SDTM	Study Data Tabulation Model		
sec	Second(s)		
SMC	Safety Monitoring Committee		
SNR	Signal-to-Noise Ratio		
SOC	System Organ Class		
t½	Terminal Elimination Half-Life		
Т3	Triiodothyronine		
T4	Thyroxine		
TEAE	Treatment-Emergent Adverse Event		
T max	Time of Maximum Concentration		
TSH	Thyroid Stimulating Hormone		
UA	Urinalysis		
Vd	Volume of Distribution		
VS	Vital Signs		

WBC	White Blood Cell
WHO	World Health Organization

## 1. **PREFACE**

The Statistical Analysis Plan (SAP) for "A Phase I, Open-Label Study to Assess Lung Pharmacokinetics and Safety of a Single Dose of Apramycin Administered Intravenously in Healthy Adult Subjects" (DMID Protocol 20-0012) describes and expands upon the statistical information presented in the protocol.

The document describes all planned analyses and provides reasons and justifications for these analyses. It also includes sample tables, listings, and figures planned for the final analyses. Regarding the final analyses and Clinical Study Report (CSR), this SAP follows the International Conference on Harmonisation of Technical Requirements for Registration of Pharmaceuticals for Human Use (ICH) Guidelines, as indicated in Topic E3 (Structure and Content of Clinical Study Reports) [1], and more generally is consistent with Topic E8 (General Considerations for Clinical Trials) [2], and Topic E9 (Statistical Principles for Clinical Trials) [3]. The structure and content of the SAP provides sufficient detail to meet the requirements identified by the Food and Drug Administration (FDA) and ICH, while all work planned and reported for this SAP will follow internationally accepted guidelines published by the American Statistical Association [4] and the Royal Statistical Society of statistical practice [5].

This document contains four sections: (1) a review of the study design, (2) general statistical considerations, (3) comprehensive statistical analysis methods for the safety and pharmacokinetic (PK) outcomes, and (4) a list of proposed tables and figures. Within the table, figure, and listing mock-ups (Appendix 1, Appendix 2, and Appendix 3), references to CSR sections are included. Any deviation from this SAP will be described and justified in protocol amendments and/or in the CSR, as appropriate. The reader of this SAP is encouraged to also review the study protocol for details on conduct of the study and the operational aspects of clinical assessments.

# 2. INTRODUCTION

Aminoglycosides are a class of antibiotics established with the introduction of streptomycin in the 1940s for the treatment of tuberculosis and have defended a strong clinical presence ever since and until today. Mainly due to the common recognition of the rapid bactericidal activity of aminoglycosides – also at very high bacterial burden – the drug class has established itself as an important therapeutic component in the treatment of serious hospital infections worldwide. Despite the introduction of several new chemical classes of antibacterial agents over the past few decades, aminoglycosides still remain an extremely important therapeutic option.

The therapeutic efficacy of standard-of-care aminoglycosides currently in clinical use is compromised by significant rates of antimicrobial resistance acquired by horizonal gene transfer. Infections with antibiotic-resistant bacteria caused an estimated 33,000 deaths in Europe in 2015 [6]. According to the CDC's *Antibiotic Resistance Threats in the United States, 2019*, more than 2.8 million antibiotic-resistant infections occur in the United States each year, and more than 35,000 people die as a result [7]. Bacterial pathogens highly resistant to various classes of antibiotics are estimated to account for a total of about 700,000 deaths annual worldwide. Without successful intervention, the burden of continued emergence and global spread of antimicrobial resistance is expected to multiply by the year 2050 [7,8]. New antibiotics are needed to adequately respond to the increasing prevalence of drug-resistant infections.

Apramycin is a mono-substituted 2-deoxystreptamine compound that is significantly different from the disubstituted 2-deoxystreptamines which include all the standard-of-care aminoglycoside antibiotics (gentamicin, amikacin, tobramycin, arbekacin, plazomicin and other) and, therefore, represents a subclass of aminoglycosides [9]. Apramycin is active against a wide variety of pathogen Gram-positive and Gramnegative bacteria including pathogens with resistance to gentamicin and all other clinical aminoglycosides of relevance.

This is a Phase 1, open-label study of a single dose of apramycin conducted at a single center. A total of 20 participants will be enrolled to one of 5 cohorts, each corresponding to a timepoint after initiation of infusion at which a single fiberoptic bronchoscopy with bronchoalveolar lavage (BAL) is performed. There will be 4 participants per cohort.

# 2.1. Purpose of the Analyses

These analyses will assess the safety and plasma and intrapulmonary PK of a single dose of 30 mg/kg apramycin administered as an IV infusion over a period of 30 ( $\pm$  5) minutes.

# **3. STUDY OBJECTIVES AND ENDPOINTS**

### 3.1. Study Objectives

#### Primary:

• To assess plasma pharmacokinetic profile of apramycin and lung penetration of apramycin in epithelial lining fluid (ELF) and alveolar macrophages (AM) after single IV apramycin dose of 30 mg/kg in healthy participants.

#### Secondary:

- To assess the safety of single IV administration of 30 mg/kg apramycin in healthy participants.
- To assess changes in otoacoustic testing.

#### Exploratory:

• To assess changes in kidney function biomarkers.

### **3.2.** Endpoints

#### Primary:

- Lung concentration and PK parameters of total apramycin:
  - ELF: Area under the concentration-time curve (AUC) from time of dosing to 24 h (AUC(0-24)), AUC from time of dosing to time t (AUC(0-t)), AUC extrapolated to infinity (AUC(0- $\infty$ )), maximum concentration (Cmax), time to maximum concentration (Tmax), terminal elimination half-life (t/2)
  - o AM: AUC(0-24), AUC(0-t), AUC(0- $\infty$ ), Cmax, Tmax, t1/2
- Plasma concentration and PK parameters of total apramycin:
  - $\circ$  AUC(0- $\infty$ ), AUC(0-t), AUC(0-24), Cmax, Tmax, t1/2, total clearance (CLT), volume of distribution (Vd) central
- Ratio of exposure parameters of Lung PK to Plasma PK:
  - $\circ \quad \text{ratio of } C_{max} \text{ in ELF over } C_{max} \text{ in plasma}$
  - o ratio of Cmax in AM over Cmax in plasma
  - ratio of AUC (0-24), AUC (0-t), and AUC (0-∞) in ELF over AUC (0-24), AUC (0-t), and AUC (0-∞) in plasma
  - o ratio of AUC (0-24), AUC (0-t), and AUC (0-∞) in AM over AUC (0-24), AUC (0-t), and AUC (0-∞) in plasma

#### Secondary:

- Type and incidence of treatment-emergent adverse events (TEAEs) and serious AEs (SAEs) to Day 30 (± 4 days) after dosing.
- Frequency of clinically significant TEAEs in physical examination (PE) findings and of changes from baseline in vital signs and clinical laboratory parameters until Day 14 (± 3 days) after dosing.
- Frequency of changes in electrocardiogram (ECG) intervals (QTcF, PR, QRS, heart rate [HR]), and of morphological changes from baseline until 24 ± 1 h after dosing.

• Type and incidence of TEAEs related to auditory (cochlear) function tests (pure-tone audiometry and distortion product otoacoustic emissions [DPOAEs]) to Day 30 (± 4 days) after dosing.

#### Exploratory:

• Changes from baseline in urinary kidney injury molecule 1 (KIM-1) and serum cystatin C concentrations until Day 30 (± 4 days) after dosing.

## **3.3.** Study Definitions and Derived Variables

#### **3.3.1.** Timepoints for Safety and PK Endpoints

Table 1 shows the analysis timepoints in the order that will appear in tables and figures along with the safety and PK endpoints measured at each timepoint for all participants. Endpoints analyzed by timepoint include chemistry clinical laboratory results (CHEM), hematology clinical laboratory results (HEM), coagulation clinical laboratory results (COAG), and urinalysis laboratory results (UA); urinary KIM-1 and serum cystatin C; vital signs (VS); ECG; ENT examination and otoacoustic (pure-tone audiometry and DPOAE) tests (listed in the table below as Audiology); and blood (plasma) PK and lung BAL PK results (see Section 3.3.2 for derivations of BAL PK parameters). Serology, toxicology, and pregnancy testing at Screening and/or Check-In will not be included in tables or figures but will be presented in listings.

Analysis Timepoint	Abbreviated Label	Endpoints
Screening	N/A	CHEM, HEM, COAG, UA, VS, ECG, Audiology
Check-In	D-2	CHEM, HEM, COAG, UA, KIM-1, Cystatin C, VS, ECG, Audiology
Day -1	D-1	VS, ECG
Day 1, Pre-Dose	0 h	CHEM, HEM, COAG, UA, KIM-1, Cystatin C, VS, ECG, Plasma PK
Maximum Severity Post Baseline	N/A	CHEM, HEM, COAG, UA, VS, ECG, Audiology
Day 1, 0.5 h Post-Dose	0.5 h	VS, Plasma PK, BAL PK
Day 1, 1 h Post-Dose	1 h	VS, ECG, Plasma PK
Day 1, 2 h Post-Dose	2 h	Plasma PK, BAL PK
Day 1, 4 h Post-Dose	4 h	VS, ECG, Plasma PK, BAL PK
Day 1, 8 h Post-Dose	8 h	Plasma PK, BAL PK
Day 1, 16 h Post-Dose	16 h	VS, ECG, Plasma PK
Day 2, 24 h Post-Dose	24 h	CHEM, HEM, COAG, UA, VS, ECG, Plasma PK, BAL PK
Day 2, 36 h Post-Dose	36 h	VS, ECG, Plasma PK
Day 3, 48 h Post-Dose	48 h	CHEM, HEM, COAG, UA, KIM-1, Cystatin C, VS, ECG, Plasma PK
Day 3, 60 h Post-Dose	60 h	VS, ECG, Plasma PK
Day 3 a	D3	Audiology
Day 14	D14	CHEM, HEM, COAG, UA, KIM-1, Cystatin C, VS, ECG, Audiology
Day 30	D30	KIM-1, Cystatin C, Audiology
a Day 3 refers to any time on Day 3.		

 Table 1:
 Analysis Timepoints for Safety and PK Endpoints

#### **3.3.2. BAL Pharmacokinetics Parameters**

There are two BAL components collected in this study, ELF (Section 3.3.2.1) and AM (Section 3.3.2.2), and apramycin concentrations and PK parameters will be measured and estimated separately in each component.

#### 3.3.2.1. Apramycin Concentrations in ELF

The estimated concentration of apramycin in the ELF component of the BAL supernatant (*Apramycin ELF*) will be calculated as follows using the urea method [10, 11, 12]:

- *Volume ELF* = *Volume BAL SUP x (Urea BAL SUP / Urea Plasma)* (equation 1)
- *Apramycin ELF = Apramycin BAL SUP x (Volume BAL SUP / Volume ELF)* (equation 2)
- Apramycin ELF = Apramycin BAL SUP x (Urea Plasma / Urea BAL SUP) (equation 3)

Where,

- *Volume ELF* is the estimated volume of ELF in the BAL supernatant (BAL SUP), which is calculated from the following parameters:
  - *Volume BAL SUP* is the measured total volume of BAL SUP after centrifugation of BAL#2 (combined volume of aspirated BAL in tubes 2, 3 and 4); and
  - *Urea Plasma* and *Urea BAL SUP* are the measured concentrations of urea in plasma and the BAL supernatant, respectively.
- *Apramycin BAL SUP* is the measured apramycin concentration in the BAL supernatant fluid.
- Note: Equation 3 is the result of merge of equations 1 and 2

### 3.3.2.2. Apramycin Concentrations in AM

The estimated concentration of apramycin in the AM component of the BAL cell pellet (*Apramycin AM*) will be calculated as follows:

- *Apramycin BAL AC* = *Concentration BAL AC x total volume of the BAL Pellet in suspension* (equation 4)
- Volume AM = BAL AC x BAL Volume  $x \% AM x 2.42 \mu L / 10^6$
- Apramycin AM = Apramycin BAL AC / Volume AM

Where,

- *Apramycin BAL AC* is the measured amount of apramycin in the total volume of alveolar cell (AC) suspension, which is calculated from the following parameters:
  - Concentration BAL AC is the apramycin concentration in BAL Pellet; and
  - Total volume of BAL Pellet in suspension (the total volume in which the cell pellet is suspended in after centrifugation of BAL#2).
- *Volume AM* is the total volume of alveolar macrophages in the BAL pellet, which is calculated from the following parameters:

(equation 5) (equation 6)

<sup>1 Reported by the study site (Alliance for Multispecialty Research [AMR])

<sup>2 Reported by the bioanalytical laboratory (KCAS)

- $\circ$  BAL AC is the counted number of total alveolar cells per mL of BAL volume;
- *BAL volume* is the measured total volume of BAL#2 (combined volume of aspirated BAL in tubes 2, 3 and 4) before centrifugation;
- $\circ$  % AM is the percentage of alveolar macrophages in total alveolar cells (BAL cell pellet); and
- $\circ$  2.42 µL is the mean cell volume of 10^6 AM cells.

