#### Listing 40: Participant Level Apramycin Concentrations in AM

[Implementation Note: Laboratory Reported Concentration will give verbatim value reported by lab (with minimal formatting, as needed) and will use a character value such as PC.PCORRES. Analysis Concentrations will report the value exactly used for analysis and will use a numeric variable such as ADNCA.AVAL. If one or more samples are excluded from NCA, two additional columns will be provided in the PK report listing: Excluded from NCA (Yes/No) and Reason for Exclusion from NCA. In the actual time column, mark out of window times with one asterisk (\*), mark substantially out of window times with two asterisks (\*\*), and mark imputed times with three asterisks (\*\*\*). Sort order: Cohort, Participant ID.]

Cohort	Participant ID	Nominal Time a (h)	Apramycin Concentration in BAL Pellet (Concentration BAL AC) (μg/mL)	Total Volume of BAL Pellet in Suspension (μL)	Number of Alveolar Cells per mL BAL Volume (BAL AC) (10  /mL)	Total BAL Volume (BAL Volume) (mL)	Percent of Macrophages in BAL Pellet (% AM) (%)	Amount of Apramycin in Total Volume of Alveolar Cells b (Apramycin BAL AC) (µg)	Total Volume of AM in BAL Pellet c (Volume AM) (mL)	Apramycin Concentration in AM d (Apramycin AM) (µg/mL)
Note: BQL = a Times are n b Apramycin c Volume AM	= Below the Que relative to time A = BAL AC = C $M = BAL AC^{3}$	uantification Limit of dosing. oncentration BAI * BAL Volume *	it. Δ AC * Total Volume % AM * 2.42 μL/10 	of BAL Pellet in Sus cells.	pension.					

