### Listing 42: Bronchoalveolar Lavage Cell Counts

[Implementation Note: Sort order: Cohort, Participant ID.]

Cohort	Participant ID	Timepoint	Total Cell Count (10  /mL)	WBC Count (10  /mL)	Macrophages (%)	Neutrophils (%)	Eosinophils (%)	Lymphocytes (%)	Epithelial Cells (%)	Other Cells (%)	If other cells observed, specify

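### The AM concentration divides drug from all pellet cells by the volume of macrophages alone, so it is too high unless the other cells hold no drug

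*SAP*

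**What the plan says.** SAP 3.3.2.2 has three steps.

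- **Amount (equation 4):** "Concentration BAL AC x total volume of the BAL Pellet in suspension". The SAP explains that this "is the measured amount of apramycin in the total volume of alveolar cell (AC) suspension". No macrophage percentage enters here.
- **Volume (equation 5):** it starts from BAL AC, which "is the counted number of total alveolar cells per mL of BAL volume", and multiplies by the BAL volume, by %AM and by 2.42 µL per 10^6 cells. The result "is the total volume of alveolar macrophages in the BAL pellet".
- **Concentration (equation 6):** "Apramycin AM = Apramycin BAL AC / Volume AM".

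Listing 40 repeats the formulas for amount and volume and heads the volume column "Total Volume of AM in BAL Pellet". Listing 42, "Bronchoalveolar Lavage Cell Counts", has columns for neutrophils, eosinophils, lymphocytes, epithelial cells and other cells beside macrophages. The literature footnote in 3.3.2.2 supports the 2.42 µL figure; no source is given for equations 4 to 6. The protocol gives no AM formula.

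AM Cmax, the AM AUCs and the AM/plasma ratios are primary (Protocol 3.2.1, SAP 3.2). They are computed from geometric means at the nominal BAL times (SAP 10.2.1), with four different participants planned at each time.

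**The concern.** The numerator and denominator refer to different cells. %AM shrinks the volume but leaves the amount untouched. The multiplication has a purpose only if other cells are expected, and Listing 42 shows that they are. Any apramycin in those cells is then credited to the macrophages, and the error can only go upward.

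At stake is the size of a primary exposure measure and its ratio to plasma. The error can also differ between participants, because it depends on each person's cell differential. The Lung PK Population (SAP 6.3.2.1) sets no minimum macrophage percentage, and SAP 10.2 keeps outliers, so a sample with few macrophages stays in a geometric mean of at most four values. No sensitivity analysis is planned.

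**Working it through.** **Inputs from the SAP:** equations 4 to 6 and 2.42 µL per 10^6 macrophages. **Assumed:** the macrophage fraction p and the relative drug content r, because neither document gives a value for either. The plan has no figure of its own to reproduce.

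**Algebra.** Let N be the number of cells in the pellet (BAL AC × BAL Volume), m the drug per macrophage, rm the drug per non-macrophage cell, and v the volume of one macrophage.

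- Amount (equation 4) = N·m·[p + r(1-p)]
- Volume AM (equation 5) = p·N·v
- SAP value (equation 6) = (m/v)·[1 + r(1-p)/p]
- True AM concentration = m/v
- SAP value / true value = 1 + r(1-p)/p, which is never below 1
- All-cell value, amount/(N·v) = (m/v)·[p + r(1-p)] = SAP value × p

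**Factor by which the SAP value exceeds the true AM concentration:**

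| p (assumed) | r = 0 | r = 0.25 | r = 0.5 | r = 1 | r = 2 |
|---|---|---|---|---|---|
| 0.95 | 1.00 | 1.01 | 1.03 | 1.05 | 1.11 |
| 0.90 | 1.00 | 1.03 | 1.06 | 1.11 | 1.22 |
| 0.80 | 1.00 | 1.06 | 1.13 | 1.25 | 1.50 |

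**Numerical check with assumed inputs.** Take a pellet at 0.5 µg/mL in 2 mL, 0.15 × 10^6 cells/mL and 100 mL of BAL. The amount is 0.5 × 2 = 1.0 µg. The all-cell volume is 15 × 10^6 cells × 2.42 µL/10^6 = 36.3 µL, so the all-cell value is 1.0/0.0363 = 27.55 µg/mL whatever p is. The SAP value is 29.00 at p = 0.95, 30.61 at 0.90 and 34.44 at 0.80. Dividing by 27.55 gives 1.05, 1.11 and 1.25, which is 1/p.

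**Effect on the summaries.** Plasma is untouched, so the AM/plasma concentration ratio rises by the same factor. At r = 1 a timepoint's geometric mean rises by 1/(geometric mean of p). For assumed fractions of 0.95, 0.90, 0.80 and 0.60 this is 1/0.800 = 1.25. AM Tmax and half-life can shift only if the factor differs between the timepoint cohorts.

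**Does the all-cell value give the other end of a range?** It is at or below m/v when p + r(1-p) ≤ 1, that is when r ≤ 1. For r between 0 and 1 the true value therefore lies between the all-cell value and the SAP value. For r above 1 both lie above the true value.

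**The case against.** The strongest case against this is that the effect is probably small and already visible.

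- **Other cells may hold little drug.** Protocol 2.1 describes aminoglycosides as charged, water-soluble molecules that cross host cell membranes poorly. That makes entry into non-phagocytic cells less likely and weakens r = 1 as a central case. It does not establish r = 0, and the SAP does not invoke it.
- **Low macrophage percentages look unlikely here.** Eligibility (Protocol 5.1 and 5.2) requires normal spirometry and no recent respiratory infection, and excludes asthma and recent nicotine use. Factors based on 50% to 70% macrophages have no support in the documents. At 90% to 95% the factor is 1.05 to 1.11 even with r = 1.
- **Equal spread by cell volume does not give 1/p.** A reader might assume it does. The factor is then 1 + w(1-p)/p, where w is the mean volume of a non-macrophage cell relative to a macrophage. It equals 1/p only if w = 1, and the SAP gives 2.42 µL for macrophages only. At p = 0.80 it is 1.06 for w = 0.25 and 1.13 for w = 0.5.
- **Sampling error is larger.** With four subjects and an assumed between-subject CV of 20%, the 95% interval for a geometric mean is already ×/÷ 1.37.
- **The data are listed.** Listing 40 shows %AM for each participant, so a reader can do the multiplication.
- **No stated decision turns on it.** The explicit criterion for enrolling T5 is detectability in BAL (Protocol 4, SAP 4.1), which rescaling cannot change. Protocol 4 also has Cmax and AUC reviewed, but sets no threshold.

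All of this limits the size and importance of the point. It does not align the numerator with the denominator or supply the missing assumption. Unlike sampling error, this error has one direction and is not reduced by averaging.

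**Conclusion.** The mismatch is real on the SAP's own equations. The AM value equals the macrophage concentration only if all pellet drug sits in macrophages, and neither document says so. Otherwise the primary AM concentration and AM/plasma concentration ratio are inflated by 1 + r(1-p)/p. The size cannot be fixed from the documents, because p and r are both unknown. For 80% to 95% macrophages and r from 0 to 1 it ranges from none to 1.25.

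Two stronger readings are tempting and not supported. One is that the inflation is at most 1/%AM; that holds only for r ≤ 1, and the documents have no data on r. The other is that the SAP value is an upper bound on the true AM concentration. It is too high only with respect to this error. Another error, such as loss of drug from cells during processing, could act downward, and processing details are left to the MOP.

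This is a cheap improvement to a primary endpoint's derivation. It gives no ground for rejecting the AM results.

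**What to change.** 1. In SAP 3.3.2.2, state that the AM value assumes all apramycin in the pellet is in macrophages.
2. In Tables 88 to 90, add as a sensitivity result the matched all-cell value, Apramycin BAL AC / (BAL AC × BAL Volume × 2.42 µL/10^6). For each participant this is the SAP value × %AM as a fraction.
3. State beside it that the two values bracket the AM concentration, with respect to this error, only if non-macrophage cells hold between no drug and the same drug per cell as macrophages. Do not label the SAP value an unconditional upper bound.

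The cost is one derived column from data already in Listing 40, with no new samples or procedures. SAP section 15 allows an addendum before final data lock. The drawback is that the all-cell value applies the macrophage cell volume to every cell type, so it is approximate and belongs beside the planned value, not in place of it.
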